## Data Analyses

### Missing Data

We have extensive preliminary data describing attrition due to mortality, which should not differ between intervention and control groups. However, we cannot exclude the possibility that missing data will be associated with intervention. We will examine the incidence of missing data by group. If imbalances are found, we will implement a series of sensitivity analyses using multiple imputations to assess the degree of bias that might be induced by missing data.

### Randomization, Intent-to-Treat, & Safety Outcomes

Participants will be assigned to the usual care control or intervention group in randomly permuted blocks of size two or four, where block sizes are selected uniformly at random. This type of randomization ensures balance across groups after every second or fourth randomization (depending on block size). The effectiveness of randomization will be assessed by summarizing the balance of baseline demographic and clinical factors across groups. The sample mean, standard deviation, and five-number summary will be used to summarize continuous variables. The count and proportion will be used to summarize categorical variables. All randomized Veterans discharged from the hospital to SNF rather than to home or hospice will be included in analyses. We will implement both intent-to-treat and per-protocol analyses.

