### Interventions and Duration

The intervention occurs during the Veteran's hospital stay (Figure 1: Phase 2). This phase includes identification of medication for deprescribing, an interview to determine Veteran preference for deprescribing, and discussion with the Veteran's inpatient treatment team. The inpatient treatment team incorporates the agreed upon final deprescribing actions in the Veteran's hospital discharge orders. The intervention ends at the point of hospital discharge.

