### Study Population and Sample Size

Eligible Veterans are age  $\geq 50$  with polypharmacy as defined by  $\geq 5$  medications based on the pre-hospital admission; ability to provide consent (or proxy); speaks English; does not reside in long-term care or receive hospice services; have a recommendation or referral to a skilled nursing facility (SNF). All eligible Veterans will be approached for consent with an original enrollment goal of 540.

The population and sample size were adjusted mid-study due to the significant enrollment and retention challenges caused by the COVID-19 pandemic. It was determined that a sample of 260 Veterans was sufficient to provide power greater than 93% for both the primary and secondary outcomes. Additionally, Veterans who were recommended SNF placement but ultimately discharged from hospital to home were approved to remain in study, which improved the study retention rate.

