## STUDY DESIGN

The study is a 3-year, randomized controlled clinical intervention trial at a singular VA medical center.

Primary Outcomes are change in total number (and/or dose) of medications including potentially inappropriate medications, number of medications associated with geriatric syndromes, and medications that contribute to anticholinergic and sedative drug burden.

Secondary Outcome is the impact of deprescribing on geriatric syndromes, medication adherence, and self-rated health status.

Implementation Science Outcomes are to identify patient and provider level barriers and facilitators as well as system-level factors required for sustainability.

Eligible Veteran population is aged 50 years or older, experiencing polypharmacy (based on pre-hospital medications), and hospitalized at Nashville VA Medical Center with a recommendation for skilled nursing facility care. Exclusion criteria include limited life expectancy (less than 6 months or hospice admission), non-English speaking, no telephone, admitted from long-term care facility, incarcerated, no valid surrogate (if unable to consent), or enrolled in another drug trial.

The timeline for the study is 3.5 years with enrollment beginning October 2019 with enrollment closing in November 2022. Final follow-up ends in March 2023.

The DROP intervention is a deprescribing protocol that considers patient and disease factors, life expectancy, goals of care, and appropriate treatment targets. Medication-specific factors such as drug-drug interactions, drug-disease interactions, and drug-specific safety profiles are also incorporated. Finally, Veteran preferences are key to final deprescribing actions by identifying the medications Veterans are willing to deprescribe. The inpatient (hospital) treatment team makes the final decision on deprescribing and incorporates the changes in the hospital discharge orders. In this intervention, deprescribing is defined as either stopping a medication or reducing the dose/frequency of a medication.

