Following enrollment, Veterans are randomized to either intervention or control groups using the REDCap randomization feature which automatically assigns allocations based on a schedule (computer generated using Mersenne-Twister), which is uploaded by the team statistician. Veterans are randomized using permuted blocks of two or four where the size of each block is selected uniformly at random. This randomization ensures balance between the groups after every second or fourth randomization.

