## Primary Outcomes – Medications

Total number of medications: Data collection begins with the Veteran's Essential Medication Review List (EMLR). After this list is abstracted from the medical record, a study NP or PharmD pulled the Controlled Substance Monitoring Database report, called non-VA pharmacies for recently filled prescriptions, reviewed non-VA medical records (i.e., outside hospital or SNF records), and interviewed the Veteran or their surrogate. We included all medications, either prescription or over-the-counter (OTC) that were administered by the following routes: oral, intravenous, intramuscular, sublingual, or ophthalmologic. Veterans (or their surrogate) were given specific prompts if they reported no OTC usage, for example, asking them if they take anything for constipation or allergies. If a patient was admitted from an institutional setting (e.g., outside hospital, SNF, ALF), we request a copy of the medication administration record from the previous 30 days. Medications are considered current/active if the Veteran took it within 30 days of hospitalization. The hospital discharge and SNF discharge medication lists, serve as the outcome data for those respective time points. During the follow-up calls, the study NP or PharmD systematically asked the Veteran for the status of each medication on the enrollment list and discharge lists to determine if and how they are taking it. Afterwards the study clinician prompted the Veteran for any new medications they may be taking.

Potentially Inappropriate Medications (PIMs): We used previously published and validated lists including the Beers criteria, the STOPP criteria, and the RASP list, which have a large degree of overlap. The total number of PIMs is the sum of medications that are found on these lists.

Drug Burden Index (DBI): This score is calculated separately for anticholinergic and sedative medications, which have been linked to functional impairment, falls, and delirium. The DBI is the sum of each individual anticholinergic/sedative medication's prescribed daily dose divided by the sum of the minimum effective dose (per the FDA minimum recommended dose) and the patient's daily dose. The DBI is calculated for all medications including OTCs. We will calculate the DBI at each timepoint, and this will capture dose reductions even when the total number of medications is not reduced.

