## **Post-Intervention Follow-Up**

The intervention ends at hospital discharge. Originally, if the Veteran discharged to any location other than SNF, they were discontinued from study. Due to retention concerns, the IRB approved the retention of Veterans who discharged home (beginning in March 2021).

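### The plan's only analysis set is limited to Veterans who went to SNF, a post-randomisation selection that conflicts with the promised intent-to-treat analysis and with keeping home discharges in the study

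*Combined protocol and SAP*

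**What the plan says.** The rule stands under Data Analyses, in Randomization, Intent-to-Treat, & Safety Outcomes: "All randomized Veterans discharged from the hospital to SNF rather than to home or hospice will be included in analyses". The next sentence reads "We will implement both intent-to-treat and per-protocol analyses". Neither set is defined there or anywhere else.

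The population changed mid-study. Study Population and Sample Size states that "Veterans who were recommended SNF placement but ultimately discharged from hospital to home were approved to remain in study" and credits this with better retention. Post-Intervention Follow-Up explains that anyone discharged elsewhere than to a SNF was at first discontinued, and dates the change: "Due to retention concerns, the IRB approved the retention of Veterans who discharged home (beginning in March 2021". Sample Size and Randomization repeats that the population was adjusted but restates no analysis set.

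On the order of events, Enrollment Procedures says "Following enrollment, Veterans are randomized to either intervention or control groups", and Interventions and Duration says "The intervention ends at the point of hospital discharge". Eligibility rests on a SNF recommendation or referral, not on arrival at a SNF.

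On the outcome, Primary Outcomes – Medications says "The hospital discharge and SNF discharge medication lists, serve as the outcome data for those respective time points".

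**The concern.** Where a Veteran goes on leaving hospital is known only after randomisation and after the whole in-hospital intervention. An analysis restricted by that event is not a comparison of the randomised groups. If DROP changes who goes to SNF, and destination is related to medication count, the SNF-only contrast mixes treatment effect with selection.

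The rule fits the original design, in which non-SNF discharges left the study. It no longer fits a study that keeps home discharges and follows them. Read literally, the Veterans kept to protect the sample add nothing to the analysis. An analyst who follows the retention sections and one who follows the analysis section would report different primary samples.

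The section heading also covers safety outcomes. The interim section compares deaths and drug-related serious events by randomised arm, so the end-of-study safety set is unclear as well.

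**Working it through.** **Order of events.** (1) SNF recommendation or referral and consent; (2) randomisation; (3) intervention, ending at hospital discharge; (4) actual destination. The analysis rule conditions on step 4.

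**Calendar.** Study Design gives "enrollment beginning October 2019 with enrollment closing in November 2022".
- Whole period: 3 + 12 + 12 + 11 = 38 months.
- From March 2021: 10 + 11 = 21 months.

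The rule omits home discharges in all 38 months. In the last 21 it omits Veterans whom the study was retaining. 21/38 = 55% is a share of calendar months, not of participants.

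**Do the data force the restriction?** Not at the first primary time point. The hospital-discharge list does not depend on going to SNF. Later time points have real gaps: 7- and 90-Day Follow-Up counts both calls from SNF discharge, and the Outcomes section indexes a random intervention effect by SNF. Home discharges have neither.

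**Bias, illustration only.** The one document input is SD 5.3 (Preliminary Data). Assumed: no true effect; 80% of controls go to SNF; 75% or 70% do so under DROP; correlation ρ of 0.3 or 0.5 between latent need for SNF and discharge medication count. Without baseline adjustment:

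bias = 5.3 × ρ × [φ(z_DROP)/p_DROP − φ(z_control)/p_control]

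The ratio φ(z)/p is 0.3500 at 80%, 0.4237 at 75% and 0.4967 at 70%, so the bracket is 0.0738 or 0.1468.

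| SNF share, DROP | ρ = 0.3 | ρ = 0.5 |
|---|---|---|
| 75% | 0.117 | 0.195 |
| 70% | 0.233 | 0.389 |

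These run against DROP. A higher SNF share under DROP would reverse the sign.

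The planned model adjusts for medications at enrolment. A trivariate-normal simulation (enrolment count, discharge count, latent SNF need; 1.5 million per arm; enrolment–discharge correlation 0.5 or 0.8) gives:
- link with destination wholly through enrolment count: within 0.01 of zero;
- destination correlated equally with both counts: 0.02 to 0.22;
- destination unrelated to enrolment count: 0.11 to 0.39 (the formula above gives 0.12 at the low end; the gap is simulation noise).

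For scale, the difference giving 93% power at 260 in a simple two-group contrast (two-sided 5%) is 3.436 × 5.3 × 2/√260 = 2.26 medications. The unadjusted range is 5% to 17% of that.

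**Power.** The plan's figure (above 93% at 260) cannot be reproduced: significance level, effect size, outcome SD and attrition for the 260 are not given. Taking exactly 93%, two-sided 5% and a two-group contrast, z(0.975) + z(0.93) = 1.960 + 1.476 = 3.436, and power(N) = Φ(3.436 × √(N/260) − 1.960). The share left out is assumed.

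| Left out | N analysed | Power |
|---|---|---|
| 0% | 260 | 93% |
| 10% | 234 | 90% |
| 20% | 208 | 87% |
| 30% | 182 | 82% |
| 40% | 156 | 76% |

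This applies only if 260 counts randomised Veterans. The original 540 counted Veterans discharged to SNF; if 260 does too, there is no such loss.

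**The case against.** The sentence may simply be left over from the original design. It says who is included and never uses the word excluded. The later retention decision and the promise of intent-to-treat could be taken to govern. That makes the ambiguity certain and a biased analysis only possible. Still, naming home and hospice as the alternatives to SNF is hard to read as anything but a restriction, and this is the operative analysis text, not a change log.

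A SNF population also has a rationale. The medication hypotheses are framed partly on SNF discharge and 90 days after it, and the handover procedure addresses SNFs. That supports a SNF-only supportive analysis. It does not make that set intent-to-treat or justify exclusions at hospital discharge.

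Nothing in the documents suggests that DROP changes destination. If SNF shares are equal by arm and destination depends on patient characteristics in the same way in both, there is no bias. The assumed inputs have no source in the documents. SD 5.3 comes from Veterans already discharged to SNF, and the planned analysis is a mixed Poisson model with a joint test over three time points, so 2.26 is only a yardstick. All of this stands. The bias and power figures show possible scale; they do not establish the defect.

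Mixed models and imputation do not answer the point. They handle missing time points for Veterans inside the set, whereas this rule removes Veterans altogether.

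**Conclusion.** The concern holds and must be fixed. From the text alone, the only stated analysis set depends on a post-randomisation event, conflicts with the retention of home discharges, and leaves the promised intent-to-treat set undefined. None of this rests on a numerical assumption.

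The size and direction of any bias cannot be determined without destination by arm. About 0 to 0.39 medications is an illustration resting on the assumed SNF shares and correlations. The fall in power to between 90% and 76% rests on assumed exclusions of 10% to 40% and on 260 counting randomised Veterans.

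**What to change.** Replace the sentence with wording such as: *The intent-to-treat analysis comprises every randomised Veteran in the assigned arm, irrespective of discharge destination, with all available time points.* Define per-protocol separately. Then state:

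1. **Home discharges, timing.** The SNF-discharge time point does not apply. Give the date from which their 7- and 90-day assessments run. If it is hospital discharge, note that with the mean SNF stay of 26.9 days (Protection Against Risks) their 90-day assessment falls about 27 days sooner after hospital discharge than for SNF Veterans.
2. **Home discharges, model.** Ensure that the SNF random effect does not delete them for want of a SNF identifier. Either omit that term for them or add a no-SNF level. The latter puts all home discharges in one cluster with a shared random intervention effect, so omission is easier to defend.
3. **Hospice and in-hospital death.** Hospice discharges contribute the hospital-discharge list and then stop, in line with Repeated Measures. In-hospital deaths are reported by arm and contribute no medication outcome.
4. **Veterans discontinued before March 2021.** Include them at hospital discharge where the list exists and its use is permitted.
5. **Reporting.** Tabulate destination by arm, before and after March 2021, and keep the SNF-discharged set as a labelled supportive analysis.
6. **Sample size.** Say whether 260 counts randomised Veterans or SNF discharges.

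The cost is SAP wording, one table, one supportive analysis, and a check on permission to use the earlier data, on which the documents are silent. The population becomes more mixed, possibly much more so if many went home. Some Veterans will contribute only the hospital-discharge time point, so the full 260 is not restored later.

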### **Safety Outcomes**

**Unplanned Healthcare Utilization:** The study team will monitor Veterans’ healthcare utilization, both at the VA and outside the VA system, after study enrollment. During the consent process, Veterans sign a release of information form that allows the team to request records from non-VA entities. We will track all emergency room visits, hospitalizations, and deaths, and these events will be adjudicated by a blinded clinician (see Safety Assessments section).

**Adverse Drug Withdrawal Events (ADWEs):** any unplanned healthcare utilization is reviewed by a blinded physician co-investigator to determine if the event was medication related, and more specifically if it was related to medication withdrawal. The standardized adjudication form includes validated scales such as the Naranjo.

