### **Methods and Timing for Assessing, Recording, and Analyzing Safety Parameters**

#### **Notification of Unplanned Healthcare Utilizations and Deaths**

Unplanned healthcare utilization (intensive care unit transfers, emergency department visits and/or hospitalizations) and deaths are monitored throughout all study phases for each Veteran. The study coordinator and research assistant share a study patient panel in the electronic health record. Any time a participant is admitted to the Nashville VA Medical Center, they are alerted. To identify if a Veteran experience an unplanned healthcare utilization at an outside hospital (OSH), the Veterans are asked at each follow-up time point if they have been to an emergency room or had an inpatient stay, and if so, at what facility. Additionally, the research assistant or study clinician reviews VISTA for any uploaded OSH records at the time of the follow-up calls. The research assistant is responsible for requesting medical records from OSHs (and SNFs) relevant to the utilization.

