## **STATISTICAL CONSIDERATIONS**

### **Sample Size and Randomization**

Existing data indicate that approximately 600 to 700 hospitalized Veterans are referred to SNF annually. Thus, we conservatively estimate that 40% (or, 240 per year) will provide consent, complete baseline assessments and discharge to SNF to yield a total consented sample of 540 across all study months. During the SNF stay, we anticipate ~5% will die, which will leave 513 (or ~256 per group) discharged from SNF. Based on preliminary data, ~15% of patients die within 90 days of SNF discharge. Thus, ~85% (or 393 total) will be alive at 90 days. In addition, we estimate we will be unable to reach ~10%, which will leave ~354 total participants (~177/group) for 90-day follow-up. The population and sample size were adjusted mid-study due to the significant enrollment and retention challenges caused by the COVID-19 pandemic.

It was determined that a sample of 260 Veterans was sufficient to provide power greater than 93% for both the primary and secondary outcomes. Finally, the study enrollment was continued for an additional 10 months beyond the original project timeline.

Participants will be randomized in a 1:1 ratio using permuted blocks of two or four, where the size for each block is selected uniformly at random. This type of randomization ensures balance across the intervention and control groups after every second or fourth randomization (depending on the size of the current block). This randomization scheme will be generated by computer using the Mersenne-Twister pseudo random number.

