### Interim Analysis and Stopping Rules

Interim analyses will be conducted to evaluate safety endpoints but will not be conducted to evaluate conditional power (futility) or to assess efficacy.

Safety will be evaluated by examining group differences in death and serious adverse events semi-annually in conjunction with scheduled DSMB meetings to evaluate the safety of the study intervention, and the associated risk-to-potential benefit ratio. The Principal Investigators will address study efficacy only at the end-of-study, and thus will not consider terminating the trial early on the basis of conditional power (futility) or evidence of efficacy. This is because firm evidence will be required to change current clinical practice, and because trials that have stopped early for efficacy often report implausibly large effect sizes (and therefore should be considered with skepticism). At the conclusion of each DSMB meeting, the Board should take into account the statistical evidence as well as practical and clinical considerations to make one of the following recommendations based on safety:

- a. Suspend enrollment due to safety concerns secondary to study intervention including:
  1. A difference in all-cause mortality between patients randomized to the deprescribing intervention versus usual care such that the DSMB deems the difference to be study-related and excessive.
  2. A difference in drug related SAEs between patients randomized to the deprescribing intervention versus usual care such that the DSMB deems the difference to be study-related and excessive.
- b. Continue Enrollment

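### The only stated analysis population depends on discharge to a SNF, so a final safety comparison that followed it would omit in-hospital deaths and Veterans discharged to hospice or home

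*Combined protocol and SAP*

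**What the plan says.** **Population.** Under Data Analyses, the section *Randomization, Intent-to-Treat, & Safety Outcomes* states: "All randomized Veterans discharged from the hospital to SNF rather than to home or hospice will be included in analyses". The next sentence reads: "We will implement both intent-to-treat and per-protocol analyses". Neither analysis gets its own population. Despite the section heading, no safety set is defined there or elsewhere.

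**Timing.** *Enrollment Procedures* places randomisation after enrolment, during the hospital stay. *Interventions and Duration* places the intervention in the same stay and ends it at hospital discharge. *Pre-Review* lists actions that stop a drug before discharge.

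**Follow-up.** *Post-Intervention Follow-Up* says that originally "if the Veteran discharged to any location other than SNF, they were discontinued from study". From March 2021, home discharges were kept in the study. No such change is stated for hospice.

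**Safety data.** *Safety Outcomes* says: "We will track all emergency room visits, hospitalizations, and deaths, and these events will be adjudicated by a blinded clinician". The section on notification of utilisation and deaths adds that "deaths are monitored throughout all study phases for each Veteran", and it also covers ICU transfers. The DSMB criterion in *Interim Analysis and Stopping Rules* is "A difference in all-cause mortality between patients randomized to the deprescribing intervention versus usual care". *Safety Monitoring and Assessments* counts a death as an adverse event only if the Veteran was not under hospice care.

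**Attrition.** *Missing Data* cites preliminary data on "attrition due to mortality, which should not differ between intervention and control groups". It then concedes that missingness could be related to the intervention, and it plans checks by group, with multiple imputation if the groups differ.

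**The concern.** Where a Veteran goes on leaving hospital is an outcome of the hospital stay. That stay includes the randomised intervention, and some drugs are withdrawn during it. An analysis set defined by destination therefore selects on something treatment could affect, and it is not intent-to-treat in the usual sense.

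This matters most for safety, which the *Précis* lists among the secondary outcomes. Readers will judge whether deprescribing in hospital was safe from the final comparison by arm. If Veterans who died before discharge, or who left for hospice or home, are absent from it, the count of serious harms is incomplete. Equal losses in the two arms would change little. If losses were more frequent on the intervention, the remaining comparison would tend to understate harm.

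**Working it through.** **Step 1. Who the rule keeps.** The inclusion rule is set beside the follow-up rule, by hospital disposition:

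| Disposition | Inclusion rule | Follow-up after hospital |
|---|---|---|
| SNF | Included; in-hospital events count | Yes |
| Home, before March 2021 | Excluded by name | Discontinued |
| Home, from March 2021 | Excluded by name | Yes |
| Hospice | Excluded by name | Discontinued; no later change stated |
| Died in hospital | Excluded by implication (never discharged to SNF) | Not applicable; death is recorded |

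The third row contradicts the amended design directly. The rule restricts which Veterans are included. It sets no start time for counting events.

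**Step 2. What planning allows for.** *Sample Size and Randomization* starts from 540 Veterans already counted as discharged to SNF. Its first loss is in the SNF: "During the SNF stay, we anticipate ~5% will die". That figure reproduces: 540 × 0.95 = 513. No rate is given for death in hospital or discharge to hospice, so the bias cannot be calculated.

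(The next step, 513 × 0.85 = 436, does not give the printed 393. That number matches 513 × 0.85 × 0.90 = 392, so the 10% unreachable appears to be taken there already. This is a separate matter; only the rates are used below.)

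**Step 3. Effect per omitted death (illustration).** Inputs: 5% die in SNF and 15% of the rest by 90 days after SNF discharge, both from the plan; 260 Veterans, assumed to be the number randomised, so n = 130 per arm.

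- Later death risk: p = 1 − 0.95 × 0.85 = 0.1925, or 130 × 0.1925 = 25.0 deaths per arm.
- 95% half-width for the risk difference: 1.96 × √(2 × 0.1925 × 0.8075 / 130) = 0.0958, or 9.6 points.
- With k extra in-hospital deaths on the intervention, the all-randomised risk is (k + (130 − k)p)/130 = p + k(1 − p)/130. The SNF-only risk stays at p.
- Understatement per death: 0.8075/130 = 0.62 points.
- Share of that arm's deaths omitted, if control has no in-hospital deaths: k/(k + (130 − k)p).

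| k (assumed) | Hidden difference, points | Share of arm's deaths omitted |
|---|---|---|
| 1 | 0.6 | 4% |
| 3 | 1.9 | 11% |
| 5 | 3.1 | 17% |

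Range over the later death risk: p = 0.10 gives 0.69 points per death (half-width 7.3), and p = 0.30 gives 0.54 (half-width 11.1). Every imbalance shown lies well inside the half-width.

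**The case against.** The sponsor has several fair replies.

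- **The sentence does not say only, and it does not mention in-hospital deaths.** The intent-to-treat promise could be read as covering them, and a section heading is thin evidence that the sentence was written for safety. This stands as far as intent goes. But the contrast with home and hospice serves no purpose except exclusion, and an analyst would have to choose between two adjacent sentences.
- **Interim review already covers all randomised.** This stands. The DSMB compares deaths by randomised group, and all deaths are also reported to the IRB. That is monitoring, however, and it sets no final analysis set.
- **No end-of-study safety analysis is specified.** True, so the consequence is conditional on such a comparison being run under this rule. The absence also means that nothing else would govern it.
- **Missingness will be examined by arm.** This is partial mitigation. The plan does not say whether Veterans outside the inclusion rule count as missing.
- **Hospice deaths are not adverse events by definition, and limited life expectancy is an exclusion at entry.** Both stand. Hospice numbers may well be small, but these deaths still belong in all-cause mortality.

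A reader might infer that all harm occurring in hospital is dropped. The documents do not support that: an ICU transfer or withdrawal event in a Veteran later discharged to SNF remains in the analysis.

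**Conclusion.** The inclusion rule is wrong as written. It selects on a post-randomisation event, contradicts the promised intent-to-treat analysis, and was not updated when home discharges were retained. Applied to a final safety comparison, it would omit Veterans who died in hospital after randomisation and those discharged to hospice or home, with their in-hospital events and, for home discharges since March 2021, their later events too.

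The gap is in the final by-arm comparison. Collection and interim monitoring of deaths are not at fault. Its size is unknown. The 0.62 points per excess death rests on the plan's SNF and 90-day death rates, 130 randomised per arm, and assumed imbalances. A reader might infer that the rule would reverse the safety conclusion or conceal deaths from oversight. Neither is supported: the illustrated effects sit inside the 9.6-point half-width, no arm imbalance is documented, and the DSMB sees deaths by randomised group. What is established is the risk of an incomplete count of serious harms.

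**What to change.** - **Inclusion rule.** Limit the SNF condition to outcomes that need a SNF stay, and correct it for retained home discharges.
- **Safety set.** Define it as all randomised Veterans by assigned arm, from randomisation, whatever the disposition.
- **Reporting.** Give by arm, with risk differences and 95% CIs: all-cause death, including deaths in hospital and under hospice; unplanned utilisation, including ICU transfer; and adjudicated withdrawal events. Add a table of hospital disposition by arm (SNF, home, hospice, died in hospital).
- **Discontinued Veterans.** Those discontinued at hospital discharge (hospice throughout, home before March 2021) contribute their in-hospital events and disposition and are then censored, with numbers per arm shown. Censoring at hospice discharge is unlikely to be independent of death, so the disposition table should be read with the mortality result.

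**Cost.** Revised wording and two or three tables. Disposition is already abstracted, deaths and ICU transfers are already monitored, and no sample-size figure changes. The downside is incomplete post-discharge follow-up for discontinued Veterans, above all for care outside the VA. The earlier rule covered October 2019 to February 2021, which is 17 of 38 enrolment months, or 17/38 × 260 ≈ 116 Veterans if enrolment were even (an assumption that COVID-19 makes doubtful). Of those, only Veterans not discharged to SNF are affected.
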